6.3 Protocol Deviations

Protocol deviations will be summarized in tables, overall for each of the three cohorts, and for the three cohorts combined. These tables will summarize the number of protocol deviations, the number and percentage of individuals with at least one protocol deviation (denominator is the number of individuals screened for the study), the number and percentage of deviations reported to local IRB/EC (denominator is number of events), and the number and percentage of each type of deviation (denominator is the number of events). All screened participants will be included.

6.4 Product Discontinuation

Product discontinuation will be summarized in tables, overall and by arm for each of the three cohorts, and overall and by arm for the three cohorts combined. These tables will summarize the number and percentage of responses to the "Primary reason for completion/discontinuation" item on the Product Discontinuation CRF. The denominator will be the number of participants in the ITT Analysis Set.

6.5 Retention

Study retention will be summarized by type of visit (mothers) or visit (infants) in tables, overall and by arm for each of the three cohorts, and overall and by arm for the three cohorts combined. Separate tables will be prepared for mother participants and infants. These tables will include the number and percentage of visits that were completed, missed, or that occurred after early termination at each visit/type of visit.

For mothers, visit expectation depended on the cohort and gestational age at enrollment of the participant, as well as the timing of their pregnancy outcome. Assuming that their pregnancy outcome had not yet occurred, all mothers were expected to complete the Week 1 phone contact (visit 3), Week 2 bi-weekly visit (visit 4), Week 3 phone contact (visit 5), and Week 4 visit (visit 6). Once the pregnancy outcome occurred, they were also expected to complete the PPO visit (visit 101) and 6-week PPO visit (visit 103). In between these visits the expected visits depended on cohort and gestational age at enrollment, and these expectations are provided in Appendix I.

Infants were expected to complete their PPO visit (visit 201), 1-week PPO visit (visit 202), 6-week PPO visit (visit 203), 6-month PPO visit (visit 204), and 12-month PPO visit (visit 205).

A completed visit is defined as an expected visit where the participant had a Follow-up Visit Summary CRF (or Infant Follow-up Visit Summary CRF for infants) with a non-missing visit date. A visit where the participant had already terminated early is an expected visit where the last date of the visit window was on or after the date of study termination. A missed visit is defined as a visit that was expected but not completed and which occurred prior to study termination. For the purposes of these calculations, a visit will only be included if the last date of the visit window occurred on or prior to the date of the participant's pregnancy outcome (e.g., a visit will be not counted as missed or expected if it was not attended and the pregnancy outcome occurred while the visit window was still open, and similarly a visit will not be counted as completed or expected if the visit occurred and then the pregnancy outcome occurred during the visit window).

Each study visit had a visit window in which it was to be completed; these windows are provided in Appendix II.

Summaries of mother retention will summarize the number and percentage of visits that were completed, missed, or that occurred after early termination at each visit/type of visit for the following types of visits:

- Phone contact visits (visit 3, visit 5, and others depending on gestational age at enrollment, see Appendix I)
- In-person visits (visit 4, visit 6, and others depending on gestational age at enrollment, see Appendix I)
- PPO visits (visit 101)
- 6-week PPO visit (visit 103)

The denominator for the percentages will be the number of expected visits.

Summaries of infant retention will summarize the number and percentage of visits that were completed, missed, or that occurred after early termination at each visit/type of visit for the PPO visit (visit 201), 1-week PPO visit (visit 202), 6-week PPO visit (visit 203), 6-month PPO visit (visit 204), and 12-month PPO visit (visit 205).

7. BASELINE DATA

Unless otherwise noted, all baseline data summaries are restricted to mothers in the analysis set.

7.1 Mother Demographics

Baseline demographic characteristics will include participant age (both as a continuous variable and as the following categories: 18-19 years, 20-24, 25-29, 30-34, and 35-40), enrollment site, ethnic group or tribe, whether or not the participant has a primary partner, number of lifetime sex partners (both as a continuous variable and as the following categories: 1 partner, 2, 3, 4, and 5+), whether or not the participant had a sexual relationship in order to get money, and the HIV status of their primary sex partner. These tables will be presented by study arm and overall for each of the three cohorts, and by study arm and overall for the three cohorts combined. These items are collected on the Demographics CRF.

7.2 Pregnancy History

Pregnancy history, as collected on the Pregnancy History CRF, will be summarized in tables, by study arm and overall for each of the three cohorts, and by study arm and overall for the three cohorts combined. These tables will summarize the number and percentage of participants who had any prior pregnancies. Among the participants with a prior pregnancy, the following will be summarized (as continuous variables):

- full term live births (≥ 37 weeks)
- premature live births (< 37 weeks)
- spontaneous fetal deaths and/or still births (≥ 20 weeks)
- spontaneous abortions (< 20 weeks)
- therapeutic/elective abortions
- ectopic pregnancies

7.3 Gestational Age

Participant gestational age at enrollment, as collected on the Pregnancy Assessment CRF, will be summarized in tables, by study arm and overall for each of the three cohorts, and by study arm and overall for the three cohorts combined. These tables will summarize the estimated gestational age at enrollment (as a continuous variable). Gestational age will be described in weeks, not in weeks and days as it is captured on the CRF (e.g., a gestational age on the CRF of 37 weeks 4 days will be defined as 37.6 weeks for the table summaries).

7.4 Baseline Medical History

Baseline medical history will be summarized in tables, by study arm and overall for each of the three cohorts, and by study arm and overall for the three cohorts combined. These tables will summarize the following (as categorical variables):

- Number and percentage of randomized participants who had any medical history event (yes or no, from Baseline Medical History Y/N CRF), and the number of events (from the Baseline Medical History Log).
- Number and percentage of participants who had a gradeable event (at least one gradeable event vs. no gradeable events, from “Is condition/event gradable” on the Baseline Medical History Log), with the denominator being the number of participants with a medical history event. The total number of gradeable events will also be summarized.
- Number and percentage of participants with a maximum severity event (Grade 4 is highest severity, Grade 1 is lowest, from “Severity grade” item on the Baseline Medical History Log), with

the denominator being the number of participants who had a gradeable event. The total number of events in each severity will also be summarized.

- Number and percentage of participants with an ongoing event (at least one ongoing event vs. no ongoing events, from “Is the condition ongoing?” item on the Baseline Medical History Log).

7.5 Prior Medication

Prior medication will be summarized in tables, by study arm and overall for each of the three cohorts, and by study arm and overall for the three cohorts combined. These tables will summarize:

- Number and percentage of randomized participants who had any prior medication (yes or no), and the number of medications.
- Number and percentage of randomized participants with at least one prior medication in each observed ATC Level 3 category, and the total number of prior medications in each ATC Level 3 category.
- Within each ATC Level 3 category, the number and percentage of randomized participants with at least one prior medication in each observed ATC Level 1 category, and the total number of prior medications in each ATC Level 1 category. The denominator for these percentages is the number of participants in the ITT Analysis Set.

Prior medications are defined as medications recorded on the Concomitant Medications Log CRF that had a “Date stopped” prior to the participant’s randomization date.

7.6 Pelvic Exam

Baseline pelvic examination findings will be summarized in tables, by study arm and overall for each of the three cohorts, and by study arm and overall for the three cohorts combined. These tables will use data collected on the Pelvic Exam CRF at the enrollment visit and will include:

- Number and percentage of participants with a pelvic exam assessment (non-missing value on the “Pelvic exam assessment” item), with the denominator being the number of participants in the ITT Analysis Set.
- Number and percentage of participants with each pelvic exam assessment result (not done, abnormal findings, or no abnormal findings), with the denominator being the number with a non-missing pelvic exam assessment result. Note that a result being missing entirely is treated as different from a result being marked as “not done”.
- Number and percentage of participants with each type of abnormal pelvic exam finding (from vulvar edema through other abnormal findings), with the denominator being the number with a non-missing pelvic exam assessment result.
 - For the abnormal vaginal discharge finding, the number and percentage of participants who had each type of abnormal vaginal discharge (slight, moderate, or pooling) will also be summarized, with the denominator being the number of participants with an abnormal vaginal discharge finding.

8. PRIMARY ENDPOINTS

An intent to treat analysis will be performed to summarize the frequency of primary endpoints (maternal safety, infant safety and pregnancy outcome) by study arm (ITT Analysis Set). An additional analysis will be conducted including only visits in which a participant has been exposed to the study product (Product Exposure Set). Analyses will be conducted separately for each of the three cohorts (including an exploratory analysis that splits Cohort 3 based on gestational age as described in Section 5), with a final aggregate analysis that will include all enrolled participants from each of the three cohorts. The number and the percentages of participants experiencing each primary endpoint will be tabulated by study arm. Each participant will contribute once in each category (i.e., only for highest severity AE for each

participant) for the calculation of event rates. Exact binomial confidence intervals will be calculated for each primary endpoint. Primary endpoint event rates will be compared to baseline estimates from MTN-042B by checking whether the baseline estimates are included in the exact binomial confidence intervals (this will not be included as part of the CSR). A secondary analysis will be performed to summarize the total number of primary and secondary safety endpoints reported per participant by study arm.

8.1 Primary Maternal Safety

The primary maternal safety endpoint is all maternal adverse events that were either serious adverse events (SAEs) or were Grade 3 or higher. These are referred to in this document as “composite AEs”.

The number and percentage of participants experiencing at least one composite AE and the exact binomial confidence intervals for those proportions will be summarized by study arm and overall for each of the three cohorts (including an exploratory analysis that splits Cohort 3 based on gestational age as described in Section 5), and by study arm and overall for the three cohorts combined. This analysis will include all participants in the ITT Analysis Set.

Secondary analyses will be conducted to further explore maternal safety. These analyses include:

1. The analyses in the preceding paragraph will be repeated using the Product Exposure Set
2. Summaries of the total number of primary maternal safety endpoints reported per participant, by study arm and overall for each of the three cohorts (including a summary of the two Cohort 3 subgroups defined in Section 5), and by study arm and overall for the three cohorts combined. This will use the ITT Analysis Set.
3. A Poisson regression model will be fitted comparing the number of primary maternal safety endpoints per participant by arm, adjusted for site, with an offset of the number of days from randomization to study product discontinuation (see “on product duration” definition in Section 6.2). This model will be fitted for all cohorts combined only, and will use the ITT Analysis Set.

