2.1 General Design Considerations

The following is a summary of Protocol Version 2.0

Short Title:	DELIVER: A Phase 3b Safety Study of the Dapivirine Ring and PrEP in Pregnant Women
IND Sponsor:	DAIDS
Funders:	Division of AIDS, NIAID, NIMH, NICHD, US NIH
Protocol Chair:	[name], MPH [name], MMed
Protocol Co-Chair:	[name], FCPaeds
Sample Size:	Approximately 550 women and their infants
Study Population:	Healthy, HIV-uninfected pregnant females, 18-40 (inclusive) years old, with an uncomplicated singleton pregnancy who are willing to be randomized to study product, and their infants
Study Sites:	MTN-042 site(s) selected by the MTN Executive Committee
Study Hypotheses:	
 • Daily use of Truvada oral tablet and dapivirine (DPV) vaginal matrix ring (25 mg) inserted once every 4 weeks will both be generally safe and well-tolerated by the participants and their fetuses/infants. • Participants who use Truvada oral tablet daily and insert the DPV vaginal matrix ring (25 mg) once every 4 weeks will experience similar distributions of pregnancy outcomes to the general population.
Study Design:	Phase 3b, two-arm, open label, multi-site, randomized (2:1) trial (DPV vaginal ring [VR], Truvada oral tablet), with onset of dosing period to occur within the following gestational age (GA) ranges: 
Cohort 1: 36 0/7 weeks – 37 6/7 weeks 150 women Cohort 2: 30 0/7 weeks – 35 6/7 weeks 150 women Cohort 3: 12 0/7 weeks – 29 6/7 weeks 150 women

Study Duration:	The total duration of study participation for each participant will vary depending on gestational age at time of enrollment and length of pregnancy prior to pregnancy outcome, and will range from approximately 12 weeks or less for Cohort 1 to approximately 36 weeks or less for Cohort 3. Participants who

become infected with HIV will continue in study follow-up with a modified study visit/procedure schedule for a minimum of twelve months. Also, infants born to MTN-042 participants will be followed for approximately 52 weeks (i.e., one year)

Study Products:

- Silicone elastomer matrix VR containing 25 mg of DPV
- Oral tablets (Truvada) containing 200 mg emtricitabine/300 mg tenofovir disoproxil fumarate (FTC/TDF)

Study Regimen:

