3. GENERAL DATA ANALYSIS CONSIDERATIONS

3.1 Analysis Set(s)

The ITT Analysis Set will consist of all enrolled and randomized women, and all enrolled infants. Participant treatment for mothers will be determined according to their randomization arm assignment. Participant treatment for infants will be determined according to their mother's randomization arm assignment.

A secondary Product Exposure Set will be used for some analyses and will differ from the ITT Analysis Set in that participants who never received any study product (per the Pharmacy Dispensation CRF) and endpoints that occur $>$ 7 days after study product discontinuation (per the Discontinuation of Study Product CRF) will be excluded.

A secondary Infant Exposure Set will be used for some analyses and will be the same as the ITT Analysis Set except that infants whose mothers never received study product will be excluded. If all enrolled and randomized mothers in a cohort received study product then the Infant Exposure Set and Infant ITT Analysis Set will be identical, and analyses using the Infant Exposure Set will not be performed.

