6.2 Treatment Exposure

As described in Section 3.1 Analysis Set(s), the Product Exposure analysis set will exclude endpoint data that occurs > 7 days after study product discontinuation, and will exclude participants who never received study product.

Study duration, infant study duration, on product duration, on study pregnancy duration, and estimated gestational age at pregnancy outcome will be summarized as continuous variable in tables, by study arm and overall for each of the three cohorts, and for the three cohorts combined.

Study duration will be calculated as the date of study exit (Study Termination CRF) minus the participant's randomization date + 1 day, unless the participant had a termination reason of "Lost to follow-up". If a participant was lost to follow-up then their study duration will be calculated as the date of their last attended visit minus their randomization date + 1 day. The last attended visit is either the last visit with a completed Follow-up Visit Summary CRF, or the last Interim Visit Summary CRF where at least one study procedure was completed (per Interim Visit Summary CRF, "What study procedures were completed at this visit? Select all that apply" item), whichever occurred last.

Infant study duration will be calculated as the date of study exit (Study Termination CRF) minus the infant's birth date + 1 day, unless the infant had a termination reason of "Lost to follow-up". If an infant was lost to follow-up then their study duration will be calculated as the date of their last attended visit minus their birth date + 1 day. The last attended visit is either the last visit with a completed Infant Follow-up Visit Summary CRF, or the last Infant Interim Visit Summary CRF where at least one study procedure was completed (per Interim Visit Summary CRF, "What study procedures were completed at this visit? Select all that apply" item), whichever occurred last.

On product duration will be calculated as the date of product discontinuation (Discontinuation of Study Product CRF) minus the participant's randomization date + 1 day. Only participants who ever received study product will be included in this summary.

On study pregnancy duration will be calculated as the date of the pregnancy outcome (outcome date on Pregnancy Outcome CRF) minus the participant's randomization date + 1 day. Only participants with an obtainable pregnancy outcome will be included in this summary.

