Visit 103 - 6-Week PPO Visit/SEV	42 days after PO	13 days prior to target	13 days after target

*The 1-Week PPO Phone Contact may be skipped if the PPO Visit occurs within the visit window for this phone contact

Table 11: Visit Timing Requirements for Infants

Visit	Target Day	Window Opens	Window Closes
V201 - PPO Visit	as soon after the PO as possible	Pregnancy Outcome	14 days after target
V202 - 1-Week PPO Phone Contact	7 days after PO	6 days prior to target	7 days after target
V203 - 6-Week PPO Visit	42 days after PO	13 days prior to target	13 days after target
V204 - 6-Month PPO Visit	183 days after PO	28 days prior to target	28 days after target
V205 - 12-Month PPO Visit	365 days after PO	28 days prior to target	28 days after target

*The 1-Week PPO Phone Contact may be skipped if the PPO Visit occurs within the visit window for this phone contact

14. APPENDIX III Residual Drug Levels Calculation

The DPV release rate per 28 days of use is calculated as:

$$rate = \frac{(conc_m - conc_r)}{days} \times 28$$

With $conc_m$ being the amount of residual drug in the manufacturer lot, $conc_r$ being the amount of residual drug in the returned ring, and $days$ being the number of days the participant should have been using the ring.

An individual ring is identified in the lab residual DPV data using the `guspec` identifier, with each individual ring having its own unique identifier. Some rings were tested multiple times and will have multiple observations with the same `guspec` value. Observations with censor values of "(A)X", "(A) X", "(B)X", "(B) X", "(B)Z", "(B) Z", or "Z" should not be analyzed. The amount of residual dapivirine in the ring ($conc_r$ above) is indicated by the value of `conc`.

Rings from the lab residual DPV data are linked to the clinical data through the Ring Insertion and Removal CRF, using the participant ID (`ptid`) and specimen collection date (`spcdt`) from the lab data and participant ID and the “Date ring returned” from the CRF data. For participants with multiple rings collected on the same date (i.e., two observations with same `ptid` and `spcdt` and different `guspec`), one ring needs to be assigned to correspond to “ring #1” in the Ring Return section of the CRF, and one to “ring #2”. In this case, the lab observation with the smaller value of `recnum` will be linked to the earlier ring return date on the CRF, and the larger value of `recnum` will be linked to the later ring return date.

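### The primary maternal safety count in Section 8.1 has no end date, so any adverse events recorded in the extended follow-up of women who acquire HIV would enter it, with no matching time for other mothers

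*SAP*

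**What the plan says.** Section 8.1 defines the endpoint without a time limit: "The primary maternal safety endpoint is all maternal adverse events that were either serious adverse events (SAEs) or were Grade 3 or higher". Each woman counts once if she has any such event, and of the primary summary it says "This analysis will include all participants in the ITT Analysis Set".

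Section 3.1 defines that set by persons, not by event time: "The ITT Analysis Set will consist of all enrolled and randomized women, and all enrolled infants". The only event cut-off belongs to the Product Exposure Set, which "will exclude endpoint data that occurs > 7 days after study product discontinuation" (Section 6.2). Section 8.1 uses it in a secondary analysis: "The analyses in the preceding paragraph will be repeated using the Product Exposure Set".

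Length of follow-up is described in Section 2.1. Participation "will range from approximately 12 weeks or less for Cohort 1 to approximately 36 weeks or less for Cohort 3". Women who "become infected with HIV will continue in study follow-up with a modified study visit/procedure schedule for a minimum of twelve months". In Appendix II the last maternal visit for Cohorts 2 and 3 is "Visit 103 - 6-Week PPO Visit/SEV", with a target of 42 days after the outcome and a window of 13 days either side. Cohort 1 has the same final visit and window. No later maternal visit is tabulated.

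**The concern.** A proportion of women who ever had an event has a clear meaning only if the period over which events are counted is stated. Here it runs, by default, to each woman's last recorded event. For most mothers that is about 6 weeks after the outcome. For a woman who acquires HIV it may be many months later, off product, and in a period that includes HIV disease and its treatment.

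Follow-up also differs by gestational age at enrollment, but that is fixed before randomization. HIV acquisition comes after randomization, is what the products are meant to prevent, and may differ between arms. The stated objective in Section 2.2 is safety associated with exposure during pregnancy. Events from a later year of follow-up in a few women do not serve that objective, and they would be mixed into the headline percentage and its exact interval.

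**Working it through.** **Inputs.** Scheduled participation is about 12 weeks (Cohort 1) to 36 weeks (Cohort 3), and extended follow-up is at least 52 weeks (both Section 2.1). Planned arm sizes are 50, 100, 150, 200 and 400 (Section 2.6). The number of women acquiring HIV and the composite event risk are not given, so both are assumed below.

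**The plan's own precision figure.** For 0 of 400, the exact upper bound is 1 − 0.025^(1/400) = 0.92%, as Section 2.6 states. For 1 of 100, the exact interval is (0.03, 5.45), also as stated. No figure in the plan is disputed on this point.

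**Ratio of observation times.** The starting point of the twelve months is not stated, so two readings are shown.
- Twelve months in total: 52/12 = 4.3 in Cohort 1 and 52/36 = 1.4 at the Cohort 3 limit.
- Twelve months added to scheduled follow-up: (12+52)/12 = 5.3 and (36+52)/36 = 2.4.

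**Upper limit on the effect.** Each woman counts once, so one seroconverter can add at most one woman with an event. The limit is 100/n percentage points per seroconverter.

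**Expected effect, for illustration.** Assume a 10% composite risk per 12 weeks, a constant rate, and adverse events recorded throughout. The risk over 52 weeks is 1 − 0.9^(52/12) = 0.367, and over 36 weeks 1 − 0.9^3 = 0.271. Expected added women per seroconverter:
- Total reading: 0.367 − 0.100 = 0.267 (Cohort 1); 0.367 − 0.271 = 0.096 (36 weeks).
- Added reading: 0.900 × 0.367 = 0.330 (Cohort 1); 0.729 × 0.367 = 0.267 (36 weeks).

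The range is about 0.10 to 0.33. On the added reading, varying the assumed risk from 5% over 36 weeks to 25% over 12 weeks widens it to 0.07 to 0.53.

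| Arm size | Limit per seroconverter (points) | Expected at 0.096 to 0.330 (points) |
|---|---|---|
| 400 | 0.25 | 0.02 to 0.08 |
| 200 | 0.50 | 0.05 to 0.16 |
| 150 | 0.67 | 0.06 to 0.22 |
| 100 | 1.0 | 0.10 to 0.33 |
| 50 | 2.0 | 0.19 to 0.66 |

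**Effect on the interval.** In Table 2, moving from 0 to 1 event raises the upper bound from 7.11% to 10.65% at n=50, and from 0.92% to 1.38% at n=400. With three seroconverters who each have a late first event, a pooled tablet arm at 15/150 (5.71, 15.96) would become 18/150 (7.27, 18.30).

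**Does the Product Exposure Set repeat settle it?** Product use ends by the pregnancy outcome (Section 2.1), so a limit of 7 days after discontinuation keeps at most 7 of the 42 days to the 6-week visit. The ITT analysis has no limit and the exposure analysis stops too early. Neither gives safety from randomization to 6 weeks after the outcome, which is the period scheduled for every mother.

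**The case against.** The strongest objection is that the problem may not arise. The SAP says only that seroconverters follow a modified schedule. Whether adverse events are collected on it, and until when, is normally fixed in the protocol, which is not at hand. This stands, and the point is conditional on such collection.

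A reader might also infer more than the text supports:
- That these women are followed for twelve further months. The SAP gives a minimum of twelve months and no starting point.
- That the late events fall outside the protocol. The extension is planned follow-up; what can be said is that it runs past the scheduled exit of other mothers.
- That the shift is large. Using 0.267 per woman, five seroconverters in a 50-woman Cohort 1 arm would add 2.7 points. But five infections among 50 women in 12 weeks is 5/(50 × 12/52) = 43 per 100 woman-years, and nothing in the SAP supports such a rate. In the 400-woman ring arm, one to five seroconverters at 0.267 each would add only 0.07 to 0.33 points.
- That a between-arm conclusion is biased. Section 2.6 plans no direct testing between arms in the primary analyses. The secondary Poisson model in Section 8.1 does compare arms on ITT events, but it is not the primary result.

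It is also fair to say that counting every recorded event is a cautious choice in a safety study, that HIV diagnoses are tabulated by arm (Section 10.6), and that Section 10.1 lists each adverse event with its onset date. A reader could therefore find the late events. That does not give the primary percentage a defined period. The SAP also describes trial conduct in the past tense, so a window set now narrows an open-label endpoint late. This is a good reason to keep the all-events proportion beside the new one.

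**Conclusion.** The point holds in conditional form. The primary maternal proportion has no stated end to its counting window, and follow-up is longer for women who acquire HIV. If adverse events are recorded in that extension, they enter the primary proportion for those women only.

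The size is nil with no seroconverters and cannot exceed one participant per seroconverter (0.25 to 2.0 points, depending on arm size). Under the illustrative constant rate it is about a tenth to a third of that limit. Pooled results would move little. A 50-woman cohort arm, which Section 8.1 also reports, could move visibly. The SAP does not support saying that late events certainly count, or that the effect is large.

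**What to change.** In Section 8.1 and the summaries in Section 10.1, count composite adverse events with onset from randomization to the 6-week post-outcome visit for every mother. If that visit is missed, count to the close of its window, day 55 after the outcome (42 + 13). Show later deaths, SAEs and Grade 3 or higher events in a separate table by arm, and report the all-events ITT proportion as a sensitivity analysis.

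Leave study duration in Section 6.2 as actual follow-up, since cutting it short would misreport how long women were observed. Report the extended HIV follow-up separately. A related point for the same edit: the Poisson model in Section 8.1 takes ITT events but uses only on-product days as its offset, so its event window and its offset should cover the same days.

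The cost is SAP wording, a date filter and one extra table. The downside is that a few late events leave the primary table, but they remain tabulated, counted in the sensitivity analysis and listed.
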